Effects of Lidocaine Spray for Pain Relief during Manual Vacuum Aspiration: A study protocol of a randomized controlled trial

Organization Protocol ID 2566/081 I

Protocol dated: 2023-10-30

Disclosure: None declared

Financial Support: UdonThani Hospital

Corresponding author: [name], Department of Obstetrics and Gynecology, UdonThani Hospital, UdonThani, Thailand. [contact], Email: [contact]

Ethics: This study protocol was approved by the UdonThani Research Ethics Committee: Number 2566/081 I

Introduction

Manual vacuum aspiration (MVA) is a frequently used gynecological procedure in many conditions, such as abnormal uterine bleeding or termination of pregnancy (1,2). Pain during the MVA procedure is often caused; when the cervix is dilated, from uterine contractions and pain due to the anxiety during the procedure (4). The pain during the MVA using a visual analogue score is an average of 4-5 (8).

There are many ways to reduce pain during vacuum aspiration, both medical and non-medical. There are many types of analgesic used, such as the nonsteroidal anti-inflammatory drugs, local anesthesia or general anesthesia (3,5,6,7) and the use of each type is often determined by each center. A common pain relief method is intravenous analgesics, such as pethidine or diazepam. However, a study reported that 78.5 % of cases had severe pain (pain score ≥ 7) during the procedure despite the intravenous meperidine being used for pain relief (7).

Lidocaine is frequently used as the local analgesics to reduce pain during cervical and uterine procedures. The common lidocaine application is paracervical block. However, serious side effects have been reported. (7) The application of cervical Lidocaine spray has proved to be effective in; endometrial sampling and intrauterine device insertion procedures (7,8). This cervical lidocaine spray method is more convenient and safer when compared with the paracervical block technique.

This study aimed to evaluate the effectiveness of using local cervical lidocaine spray for pain relief during MVA procedure when compare with the placebo.

Methods and analysis

Study setting & design

This study is a randomized, double blinded, placebo-controlled trial conducted at UdonThani Hospital, UdonThani, Thailand.

Participants/Inclusion and Exclusion criteria

In this trial, the inclusion criteria is that the women are to be aged between 20 and 60 years and who have an indication for requiring a MVA procedure. The exclusion criteria are women who have; an allergy or hypersensitivity to lidocaine, the symptoms of reproductive tract infection or urinary tract infection, abnormal vital signs such as low blood pressure or fever, chronic liver or kidney disease.

Study methods

The study details will be explained to the participants and their written informed consent will be obtained before their participation. The randomization will be performed by computer generated numbers that were prepared in opaque, sealed envelopes. The eligible patients will be randomly assigned into two groups by the researchers. Group 1 received 4 puffs of 10% Lidocaine spray without adrenaline and intravenous opioid analgesic, group 2 received 4 puffs of the placebo (normal saline with the similar packaging (should this be) to the 10% Lidocaine spray) and intravenous opioid analgesic.

The MVA procedure will be performed at the gynecological ward. The patients will be informed about the procedure. The basic characteristics and the associated factors will be recorded in the case record form. The steps of the MVA procedure are as follows:

1. Participants lie in the dorsal lithotomy position.

2. The 50 mg intravenous Meperidine is used for analgesia 15-20 minutes before the operation.
3. The skin is cleaned using povidone iodine solution, then the sterile cloth is applied.
4. A speculum is inserted and the vagina is cleaned with a povidone iodine solution.
5. The lidocaine spray (10% Lidocaine spray without adrenaline) or the placebo (normal saline spray) is sprayed (4 puffs) onto the cervix. (9)
6. A tenaculum is clamped at the 2 and 10 o'clock positions of cervix. The pain score using visual analogue scale is assessed by the researcher.
7. The length of the uterine cavity is measured by a uterine sound.
8. The Karman cannula with the vacuum syringe is used to aspirate endometrium tissue in the uterine cavity. The size of cannula depends on the cervical os. The pain score is assessed by the researcher again.
9. After the procedure is completed, bleeding is checked and the device is removed. The overall pain score is assessed again.
10. The pain level is checked at 30 minutes after the procedure
11. The side effects of procedure are recorded such as nausea vomiting , hypotension ,abnormal bleeding, dizziness

To ensure confidentiality in the collection of the data, the subject identification code will only be used in the case record form. The information is recorded and entered in the Stata file and then is analyzed.

Blinding

Both patients and investigators are blinded in this study. The Lidocaine spray and placebo will be prepared by the pharmacists in similar packaging and place in opaque envelopes with the allocated number.

Outcomes

The primary outcome is to compare the pain scores during the operation between both groups. The secondary outcome is to evaluate the side effect of the local Lidocaine spray. The visual analog scale (scale 0-10) is used for pain evaluation. The data will be presented as continuous scores (with mean and standard deviation (SD), or median with interquartile range (IQR)) and/or as dichotomized scores (with number and percentage). All outcomes will be compared between groups using the mean difference and 95% confidence interval and the relative risk with 95% confidence. Analyses will be based on the intention-to-treat approach.

Sample size

Sample size is calculated by the Stata statistic program using the formula to test the two independent proportions. The proportion in the treatment group is 0.785, the proportion in the control group is 0.6(8). The calculated sample size is 97 per group and the 10% drop-out rate is added, the total sample size is 214.

Statistical analysis plan

The baseline characteristics of the participants will be compared between the Lidocaine spray and the placebo groups using unpaired T-test, Mann-Whitney U test, Chi-square test or Fisher's exact test when appropriate. A two-sided P-value <0.05 will be considered statistically significant. For the primary and secondary outcomes, we will report the mean difference of pain scores between groups with the 95% confidence interval for the continuous outcome and the relative risk with the 95% confidence interval for the dichotomous outcomes. For the main analysis, all outcomes will be analyzed using unpaired t test or logistic regression analysis. All analyses will be performed according to the intention-to-treat principle using Stata statistical program version 13.

Ethics

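### The secondary outcome is the spray's side effects, but step 11 records those of the procedure with no pre-spray check: the arms stay comparable, yet the planned relative risk is diluted towards 1

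*Combined protocol and SAP*

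**What the plan says.** The Outcomes section states: "The secondary outcome is to evaluate the side effect of the local Lidocaine spray".

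The only step that collects such data is step 11 of the MVA sequence in Study methods: "The side effects of procedure are recorded such as nausea vomiting", followed by hypotension, abnormal bleeding and dizziness. It follows step 10, "The pain level is checked at 30 minutes after the procedure", but has no recording window of its own. The protocol text gives no symptom check before the spray, no rule for what counts as new, and no definition of abnormal bleeding.

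Three other statements bear on what the list will pick up:

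- Step 2: "The 50 mg intravenous Meperidine is used for analgesia 15-20 minutes before the operation". The spray comes later, at step 5. Both groups receive the opioid.
- The Introduction says that MVA is used "in many conditions, such as abnormal uterine bleeding or termination of pregnancy". Any woman in the age range with an indication may enter, and bleeding is not an exclusion. Low blood pressure is.
- The Statistical analysis plan compares dichotomous outcomes by relative risk with a 95% confidence interval. It names no risk difference for them.

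**The concern.** The objective concerns one exposure, the spray, but the data item covers everything that happens around the procedure. A woman who becomes nauseated or dizzy after meperidine and before step 5 has a symptom that the spray cannot have caused, yet nothing in step 11 keeps it out. The same holds for a woman whose abnormal bleeding is the reason she is there. A reaction of the cervix or vagina to the spray, by contrast, is recorded only if someone thinks to write it in.

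Events unrelated to the spray should occur about equally in both arms. Adding the same background to both arms brings the ratio of the two risks closer to 1 and makes the comparison noisier. The trial could then report no difference in side effects when it had little ability to see a spray effect of moderate size.

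**Working it through.** **The plan's own figure.** The sample size of 97 per group reproduces exactly for proportions 0.785 and 0.6, two-sided 5%, pooled variance and 80% power (the power is not stated; 80% is the value that gives 97). Then 97 × 1.10 = 106.7, rounded to 107, and 2 × 107 = 214, as stated. This calculation serves the primary outcome. No figure is given for side effects, so everything below rests on assumed rates.

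**Model.** Let *b* be the risk of a recorded event from the condition, opioid or procedure, equal in both arms. Let *p* be an independent risk of an event arising after the spray. The recorded risk is 1 − (1 − b)(1 − p). The relative risk (RR) is the ratio of the two recorded risks. The risk difference (RD) is (1 − b) times the difference in *p*.

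**Scenario 1.** Assume *p* = 10% with lidocaine and 2% with placebo, with 107 per arm. Power is the two-sided 5% normal approximation for two proportions. At b = 30%:

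- lidocaine: 1 − 0.70 × 0.90 = 0.370
- placebo: 1 − 0.70 × 0.98 = 0.314
- RR = 0.370 / 0.314 = 1.18; RD = 0.056

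| Background b | Lidocaine | Placebo | RR | RD (points) | Power |
|---|---|---|---|---|---|
| 0% | 10.0% | 2.0% | 5.00 | 8.0 | 70% |
| 5% | 14.5% | 6.9% | 2.10 | 7.6 | 44% |
| 10% | 19.0% | 11.8% | 1.61 | 7.2 | 31% |
| 20% | 28.0% | 21.6% | 1.30 | 6.4 | 19% |
| 30% | 37.0% | 31.4% | 1.18 | 5.6 | 14% |
| 40% | 46.0% | 41.2% | 1.12 | 4.8 | 11% |

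The RD shrinks much less than the RR, but its interval widens. The 95% half-width is 1.96 × √[(0.10 × 0.90 + 0.02 × 0.98)/107] = 6.3 points with no background. At b = 30% it is 1.96 × √[(0.370 × 0.630 + 0.314 × 0.686)/107] = 12.7 points.

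**Scenario 2, a different set-up.** Let the placebo risk be the background alone, let the spray add an independent 10%, and use 97 per group. Moving b from 5% to 30% takes the RR from 0.145/0.05 = 2.90 to 0.37/0.30 = 1.23, the RD from 9.5 to 7.0 points, and power from 61% to 18%. The direction is the same.

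**What a pre-spray check could recover.** It removes only what is present before step 5. Suppose half of a 30% background in scenario 1 is present by then, leaving b = 15%. The risks are 1 − 0.85 × 0.90 = 0.235 and 1 − 0.85 × 0.98 = 0.167. RR rises from 1.18 to 1.41, RD from 5.6 to 6.8 points, and power from 14% to about 24%. The no-background row is out of reach for any recording scheme, because sounding and aspiration (steps 7 and 8) follow the spray and opioid effects can begin after it.

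**The case against.** The strongest reply is that this is a randomised, blinded trial in which "group 2 received 4 puffs of the placebo" and the same opioid and procedure as group 1. Recording all events and comparing arms is a sound approach to safety: an excess with lidocaine can be attributed to the spray without judging single events. This stands. A reader might infer that counting opioid symptoms or presenting bleeding biases the comparison. It does not, because those events are balanced by design. What is lost is specificity and precision.

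Several further points also stand:

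- **Scale.** The severe fall is on the RR scale. Numbers and percentages are planned too, so the absolute difference will be visible, although no interval for it is specified.
- **Pooling.** The documents do not say that symptoms are combined into one any-event outcome. Analysed singly, each symptom is diluted only by its own background.
- **Open list.** The items in step 11 are examples, so a local reaction may be recorded; it is only unprompted. Nausea, dizziness and hypotension could also reflect systemic effects of the drug, so the list is not irrelevant to the spray.
- **Background partly handled.** Low blood pressure at entry is excluded. Bleeding is checked after aspiration at step 9, so counting the presenting bleeding is a possible reading, not a stated rule.
- **The case record form is not in the documents.** It holds baseline characteristics and associated factors that the protocol does not list, so the missing pre-spray check is an absence from the protocol text only.

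A reader might also infer that a null result would support the Introduction's description of the spray as the safer method. That description is relative to paracervical block, and this trial has no block arm, so it could not support it however events were recorded.

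**Conclusion.** The point holds as a mismatch between the stated secondary outcome and the data collected for it, with loss of specificity and precision as the consequence. The direction, towards a relative risk of 1, does not depend on the assumed rates. The size does: it rests on side-effect rates that the documents do not give, on independence of background and spray effects, and on pooling the symptoms into one yes/no outcome, which the plan does not state. The tabulated figures are illustrations, not estimates for this trial. The primary outcome and the sample size are unaffected. A change is worthwhile because it brings the data closer to the objective at very little cost, not because the present comparison is invalid.

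**What to change.** 1. On the case record form, record each listed symptom and the bleeding status immediately before step 5.
2. Add a tick-box for local cervical or vaginal reaction.
3. In Outcomes, define the secondary outcome per symptom as an event that is new or worse after the spray, up to the existing 30-minute check.
4. In the Statistical analysis plan, report the risk difference with its 95% confidence interval beside the relative risk.
5. State that opioid and procedure events starting after the spray are still included. Attribution to the spray therefore rests on the between-arm comparison, and a null result should be read from the confidence interval, not from the P-value alone.

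The cost is a few tick-boxes and a few sentences of text, with no added visit. The downside is a few more questions before the spray.

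### The 97 per group comes from a two-proportion formula for an unnamed event, while the primary outcome is pain scores with no reading, analysis scale or cut-off named as primary

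*Combined protocol and SAP*

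**What the plan says.** **Sample size.** "Sample size is calculated by the Stata statistic program using the formula to test the two independent proportions". The inputs follow: "The proportion in the treatment group is 0.785, the proportion in the control group is 0.6(8", where the 8 is a reference number. The result is 97 per group, and 214 in total after adding 10% for drop-out. The section gives no event, cut-off or power.

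**Outcomes.** "The primary outcome is to compare the pain scores during the operation between both groups". The instrument is a 0-10 VAS. Scores may be shown as continuous values "and/or as dichotomized scores (with number and percentage"), and no cut-off is given. Then: "All outcomes will be compared between groups using the mean difference and 95% confidence interval and the relative risk with 95% confidence".

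**Statistical analysis plan.** Significance is two-sided at 0.05. One sentence links the mean difference to pain scores as the continuous outcome, and the relative risk to dichotomous outcomes. The next reads: "For the main analysis, all outcomes will be analyzed using unpaired t test or logistic regression analysis".

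**Study methods.** Pain is scored when the tenaculum is applied (step 6: "The pain score using visual analogue scale is assessed by the researcher"), at aspiration (step 8), as an overall score after completion (step 9), and 30 minutes later (step 10). None is called primary.

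**Introduction.** As background, citing reference 7, "a study reported that 78.5 % of cases had severe pain", defined as a score of 7 or more, despite intravenous meperidine.

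**The concern.** A sample size should belong to the comparison that will decide the trial. Here the calculation concerns the share of women with some event, the primary outcome is a set of scores, and the text does not join the two.

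Two things are at stake. The first is the 5% level. If pain may be tested at more than one reading, and perhaps on more than one scale, each at 0.05, the overall error rate exceeds the stated level unless one comparison is fixed in advance. The second is the planning assumption. The event, its direction and its source have to be pieced together from the Introduction, and the pieces conflict.

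**Working it through.** **1. The plan's own figure.** Inputs: p1 = 0.785 and p2 = 0.6 (Sample size); two-sided alpha 0.05 (Statistical analysis plan); power not stated, 80% assumed. The pooled-variance formula is

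n = [1.960 × √(2p̄(1−p̄)) + 0.842 × √(p1(1−p1) + p2(1−p2))]² / (p1−p2)²

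- p̄ = 0.6925, so 2p̄(1−p̄) = 0.4259; p1(1−p1) + p2(1−p2) = 0.4088; (p1−p2)² = 0.034225.
- n = (1.279 + 0.538)² / 0.034225 = 96.48, rounded up to 97.
- Drop-out: 97 × 1.10 = 106.7, so 107 per group and 214 in total.

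Both figures reproduce. At 90% power the answer would be 129, so 80% is the likely choice. The formula is symmetric, so swapping the arm labels leaves 97 unchanged.

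**2. Which event, and in which direction.** The only 78.5% elsewhere in the document is the Introduction's proportion with severe pain under meperidine, with no mention of lidocaine. If that is the event, the labels as printed give a risk ratio of 0.785/0.60 = 1.31 for lidocaine; swapped, it is 0.60/0.785 = 0.76. The Introduction credits 78.5% to reference 7, while the Sample size sentence cites reference 8.

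**3. Which analysis.** There are two readings of the analysis text.
- *t test for pain, logistic regression for side effects.* The sentence linking the mean difference to pain scores favours this. No planned pain analysis then matches the two-proportion calculation. Steps 6 and 8 remain open, and arguably the step 9 overall score.
- *Both methods for pain.* The Outcomes section allows this, since it permits dichotomized scores and applies both effect measures to all outcomes. The analysis scale and the cut-off are then open too.

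**4. Effect on the 5% level.** For two independent tests the rate is 1 − 0.95² = 9.75%; correlated readings give less. Null trials were simulated with 97 per arm and normal scores rounded and limited to 0-10. SD 2.5, means 4.5 and 7.5, and correlations 0.5 and 0.7 are all assumed. A pooled two-proportion test at 7 or more stood in for logistic regression. The table shows how often at least one test is significant.

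| Tests at steps 6 and 8 | Mean 4.5 (corr. 0.5; 0.7) | Mean 7.5 (corr. 0.5; 0.7) |
|---|---|---|
| t test only | 9.2%; 8.5% | 9.1%; 8.7% |
| t test or score ≥7 | 15.1%; 14.4% | 13.9%; 13.2% |

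With SD 2 or 3 and correlation 0.6, the second row stays between 13.6% and 15.2%.

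**5. Power if the primary is the mean score.** The document gives no SD and no target difference.
- By the t distribution, 97 per group has 80% power for 0.404 SD. That is 0.81, 1.01 or 1.21 points at assumed SDs of 2, 2.5 or 3.
- Under a normal model with one cut-off, 0.785 against 0.60 implies a shift of 0.789 − 0.253 = 0.536 SD. Then 0.536 × √(97/2) = 3.73, and Φ(3.73 − 1.96) = 0.96, so the t test has about 96% power. Rounding and limiting scores to 0-10 lowers this to 94-95% (SD 2 to 3 assumed).

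**The case against.** The best defence is that the Statistical analysis plan all but settles scale and test: mean difference for pain scores, relative risk for dichotomous outcomes. On that view only the reading is open, and the relevant error rate is the lower one. This is a fair reading and probably the intended one. It does not rule out testing dichotomized pain scores, which the Outcomes section expressly permits, and it leaves the mismatch with the sizing formula in place.

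It can also be said that the error rates need a rule the document never states, namely claiming success on any significant result. That stands: the rates are illustrative, and the case does not rest on their exact size.

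A reader might go further in four ways that the document does not support.
- *That 97 is wrong.* It reproduces exactly.
- *That the trial is underpowered.* Under the planning rates and a normal model, the t test has more power than the comparison used for sizing.
- *That the planning assumption cannot be traced.* The Introduction gives the same percentage, an event, a cut-off and a meperidine background that both arms share, so the event can be inferred. What is missing is a statement of it and agreement on arm and source.
- *That no scale is named.* The VAS is; what is not fixed is whether it is analysed as a mean or as a proportion.

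**Conclusion.** The point holds and should be corrected before analysis. The sample size is derived for a binary event that the outcome and analysis text does not define. The primary outcome is plural, with no reading, analysis scale or cut-off fixed. If the inferred event is right, the printed arm labels contradict the trial's aim, though N is unaffected.

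If any significant result were claimed, the 5% level would become about 8 to 9.5% with a t test at two readings, and about 13 to 15% if a comparison at 7 or more were added. These figures rest on the assumed score distribution, SD and correlation. The mismatch and the missing primary reading rest on the text alone.

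**What to change.** Before any unblinded analysis, issue a dated amendment to the Outcomes, Sample size and Statistical analysis plan sections that does the following.

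1. Names one primary reading, one analysis scale (with a sourced cut-off if dichotomized) and one test at two-sided 5%. The other readings and the other scale become secondary.
2. Names the event behind 0.785 and 0.6, reconciles the arm labels and citations with the Introduction, and states the power actually used (80% reproduces 97).
3. If the primary is the mean score, says that N was derived from proportions and gives the detectable difference: 0.40 SD at 97 evaluable women per group, turned into points with a sourced SD.

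N stays at 214 if only the labels change. If a proportion itself changes, keep N and restate the power.

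The timing needs a statement from the sponsor. The Ethics section places submission of the protocol ahead of the analysis, but the Authors' contributions section describes the analysis in the past tense. Neither shows whether unblinded results have been seen. If they have, the report should say so and give all intra-operative readings and the step 9 overall score on both scales, as comparisons not ranked in advance.

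The cost is one amendment and no extra patients. One scale and the other readings lose primary status. Choosing the mean leaves N derived for a different endpoint and needs a sourced SD; choosing the proportion keeps the derivation but uses less of the information in the score.

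### The plan promises a relative risk for dichotomous outcomes, but the only main-analysis method it names that fits them is logistic regression, which estimates an odds ratio

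*Combined protocol and SAP*

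**What the plan says.** The effect measure is stated twice. The Outcomes section says "All outcomes will be compared between groups using the mean difference and 95% confidence interval and the relative risk with 95% confidence", and the Statistical analysis plan section promises "the relative risk with the 95% confidence interval for the dichotomous outcomes".

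The method comes in the next sentence of that section: "For the main analysis, all outcomes will be analyzed using unpaired t test or logistic regression analysis". No other method is named for outcomes. Chi-square and Fisher's exact tests appear only in the sentence on baseline characteristics, which are compared "using unpaired T-test, Mann-Whitney U test, Chi-square test or Fisher's exact test when appropriate".

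Two kinds of outcome can be dichotomous:

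- **Side effects.** The Outcomes section says "The secondary outcome is to evaluate the side effect of the local Lidocaine spray". Step 11 of the Study methods says "The side effects of procedure are recorded such as nausea vomiting" and goes on to other events of the same yes/no kind.
- **Pain.** Scores may be presented as continuous "and/or as dichotomized scores (with number and percentage", and the sample size rests on two proportions.

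**The concern.** A logistic model's treatment coefficient is a log odds ratio. The plan gives no step from it to a relative risk: no 2x2 calculation, no risk-ratio model and no conversion of the fitted model. As written, the named method does not deliver the promised measure.

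Two things are at stake. When events are common, the OR lies much further from 1 than the RR, so a reader expecting an RR would misjudge the effect if shown the model's own estimate. When events are rare and one arm has none, the maximum likelihood estimate of the OR is not finite, and the plan gives no fallback.

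**Working it through.** **Inputs.** Planning proportions, from Sample size: "The proportion in the treatment group is 0.785, the proportion in the control group is 0.6(8". From the same section: 97 per group, 10% drop-out, 214 in total, so 107 per arm. Two-sided 5% level, from the Statistical analysis plan. Power is not stated; I assume 80%. Side-effect rates are not given, so every such rate below is an assumption. Ratios of the planning proportions are taken as lower over higher, so they do not depend on which arm carries which label.

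**1. The plan's own figure.** With mean proportion (0.785 + 0.60)/2 = 0.6925,

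n = [1.960·√(2 × 0.6925 × 0.3075) + 0.842·√(0.785 × 0.215 + 0.60 × 0.40)]² / 0.185² = 96.5, which rounds up to 97 per group.

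97 × 1.10 = 106.7, so 107 per arm and 214 in total. The figure is reproduced.

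**2. RR and OR at the planning proportions.**

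- RR = 0.60/0.785 = 0.764
- OR = (0.60/0.40)/(0.785/0.215) = 0.411

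Read as an RR, the OR would suggest a 59% relative reduction instead of 24%.

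**3. The same contrast in counts**, 64/107 vs 84/107, with 95% CIs on the log scale:

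| Measure | Standard error of the log | Estimate (95% CI) | Wald p |
|---|---|---|---|
| RR | √(1/64 − 1/107 + 1/84 − 1/107) = 0.0940 | 0.76 (0.63 to 0.92) | 0.0038 |
| OR | √(1/64 + 1/43 + 1/84 + 1/23) = 0.307 | 0.41 (0.22 to 0.74) | 0.0035 |

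The test hardly changes; the estimate does.

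**4. Uncommon events**, assumed 4% vs 2%: RR = 2.00; OR = (0.04/0.96)/(0.02/0.98) = 2.04.

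**5. One arm empty**, 107 per arm. The logistic coefficient grows without limit. For 0 vs 7 the fit stopped at −21.9 with a standard error of about 12,665, so the Wald p is 0.999. It is also 0.999 for 0 vs 5 and 0 vs 6. The likelihood-ratio test from the same model still works: p = 0.0016 for 0 vs 7. Fisher's p is 0.060 for 0 vs 5, 0.029 for 0 vs 6 and 0.014 for 0 vs 7, so six is the smallest count at which it falls below 0.05.

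**6. How often a Wald test would miss what Fisher's test detects.** This needs one empty arm and at least 6 events in the other. With X binomial (107, p):

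P = (1 − pA)^107 · P(X_B ≥ 6) + (1 − pB)^107 · P(X_A ≥ 6)

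| Assumed true rates | Probability |
|---|---|
| 1% in both arms | 0.05% |
| 2% in both arms | 0.5% |
| 3% in both arms | 0.8% |
| 5% in both arms | 0.4% |
| 2% vs 5% | 5% |
| 0.5% vs 5% | 26% |

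**7. A test and interval that agree.** For 0 vs 5 the score test uses the pooled proportion 5/214 = 0.02336:

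z = (5/107)/√[0.02336 × 0.97664 × (2/107) × (214/213)] = 2.257, p = 0.024.

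The Miettinen-Nurminen upper limit for the RR is 0.76, which excludes 1, as the test does. Fisher's p of 0.060 beside that interval would not agree with it.

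**The case against.** The strongest reply is that the two sentences do different jobs: one fixes the estimate (an RR, from the 2x2 counts) and the other names the test (logistic regression, for the p-value). On that reading nothing conflicts, and the work is feasible. This is a possible reading, but it is not written; the plan gives no route to the RR or its interval. It makes the fault minor without removing it.

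It is also fair that the plan names no Wald test. An analyst using the likelihood-ratio test would not lose the difference in the 0 vs 7 example, though the model would still give no finite estimate. That part of the point is therefore conditional.

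A reader might infer that the trial will report odds ratios under the name of relative risks. The documents announce no such step. A reader might also infer that the conclusions on pain are unsafe. If pain is analysed as a continuous score, the t test and mean difference are untouched. If it is dichotomised, the p-value hardly moves.

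**Conclusion.** Wrong as written, and minor. The named method does not estimate the promised measure. The gap is large (0.41 against 0.76) only for common events, in practice if pain is dichotomised, which the plan leaves open. For uncommon side effects with events in both arms it is negligible.

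The empty-arm problem is real but rests on assumed rates. A reader might take the chance of exactly one empty arm as its size: with an assumed 1% in both arms that is 2 × 0.341 × 0.659 = 45%, where 0.341 = 0.99^107. That figure describes how often the logistic estimate would not be finite. It does not describe a missed difference, because equal rates leave none to miss. The relevant probability is 0.05% to 0.8% at equal rates of 1% to 5%. It becomes material only if the true rates differ widely, and only if a Wald test is used.

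**What to change.** Replace the sentence that names the main analysis with:

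> Continuous outcomes will be compared by unpaired t test (mean difference, 95% CI). Dichotomous outcomes will be compared by the unadjusted relative risk, lidocaine versus placebo, from the 2x2 table, with the score (Miettinen-Nurminen) 95% CI and the matching score test, including when one arm has no events. If neither arm has events, only the counts and the risk difference with its CI will be reported.

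The plan names no covariates, so an unadjusted RR is enough. An empty arm still leaves an RR estimate of 0, or none that is finite if the placebo arm is the empty one. The interval remains informative at one end: for 5 vs 0 the lower limit is 1/0.756 = 1.32.

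The cost is a short change to the text, with no extra data and no change to sample size or alpha. One small downside is that the score test is less conservative than Fisher's exact test with few events (0 vs 5: 0.024 against 0.060). I have not checked whether the Stata version named in the plan gives the score interval directly; the trial statistician should confirm this before the wording is fixed.
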